## Contribution of the HSHS follow up study to knowledge and NHS policy and practice

This follow-up study will provide key evidence regarding the potential impact of an early childhood intervention. Specifically, in whether the intervention prevents some of the well-established later risks associated with early onset behaviour problems which impact on children, families, health services and schools. Behaviour disorders are more marked at age 7 (19). Additionally, as children navigate the transition to school the associated psychosocial, behavioural, and cognitive challenges are expected to intensify existing behaviour problems and undermine children's academic competence (20).

Early intervention and prevention programmes targeting parenting behaviour have become a key focus of domestic policy. The NHS Five Year Forward View for Mental Health (21), the NHS Long-Term Plan (22), the Healthy Child Programme (23), the 2017 Green paper on children and young people's mental health (13), and the 2019 Green paper on advancing health through

Healthy Start, Happy Start: Long-term follow-up - Study Protocol v 1.2

Protocol No: 1.2

Sponsor: University of Cambridge

V 1.2[tbc]

prevention (24) all emphasise the need for timely provision of intervention to children and their families, and the economic benefits of very early intervention. NICE highlights the importance of selective prevention and early intervention for children at risk of early onset conduct disorders, but the evidence currently only supports this provision from three onwards. The current study will provide key evidence to address this important, and potentially costly, gap in knowledge (25).

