## 2.3.3 Exploratory endpoints/outcomes

- 1. Executive function assessed using computerised computer tasks
- 2. Language development assessed using a pictorial measure of vocabulary
- 3. Prosocial behaviour assessed using a dolls play story stem battery
- 4. School enjoyment assessed using a short questionnaire
- 5. Parents long-term reflections on receipt of the intervention using a brief questionnaire
- 6. Child health and education outcomes measured using routinely collected data from the Department for Education National Pupil Database (Early Years Foundation Stage assessment; Children in need referrals; Special educational needs; Pupil absences and exclusions) and to databases maintained by the National Health Service, including NHS Digital

Healthy Start, Happy Start: Long-term follow-up - Study Protocol v 1.2

Protocol No: 1.2

Sponsor: University of Cambridge

V 1.2[tbc]

(Hospital Episode Statistics for attendance at accident and emergency and outpatient services as well as hospital admissions)

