## 6.1 Recruitment and response monitoring

A total of 300 families (child aged 12-36 months, and one or two participating caregivers) were recruited into the Healthy Start, Happy Start trial between July 2015 and July 2017. Five and 24-month follow-up data were collected between December 2015 and July 2019, with outcome data collected at one or both post-intervention time points for 294/300 (98%) families. There was a very high retention rate at 24-month follow-up (N = 282; 94%) and it is anticipated that a minimum of 85% of the original sample (N = 256) will re-engage at the 5-year follow-up.

On the advice of the patient and public involvement group, all families who were randomised into the original trial will be notified of the opportunity to participate in the 5-year post-randomisation assessment using a multipronged approach. Families will first be informed of the assessment via email and post, and then contacted via telephone to discuss the visit. This comprehensive approach to participant reengagement may circumvent issues related to changes to participant contact details since the last study contact.

Even if the recruitment rate is lower than the estimate of 85%, previously collected data will be used to provide additional statistical power for analyses (previously collected data from at least two time points is available for over 95% of the sample). Due to the longitudinal analysis being used and previously high retention rate, with 200 participants (67%) simulations demonstrate that it will still be possible to obtain a high expected posterior probability of 90% or greater if the treatment effect is sustained. However, low retention would raise concern for the introduction of bias if unequal between arms and concerns for reducing the generalisability of the results. A lower bound of 70% recruitment rate will initially be set (families successfully contacted and scheduled for the assessment visit). These numbers will be monitored on a monthly basis and the SSC will be notified if recruitment is consistently below 70% for any period of the study. A stop-go decision will

Healthy Start, Happy Start: Long-term follow-up - Study Protocol v 1.2

be made after 6 months of recruitment, as follows:

- Minimum rate recruited (contacted and scheduled) at Month 10 of study (after 6 months of recruitment) = 70% of those approached
  - If ~<70% stop study

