## 6.1.1 Participant identification

Participants will be contacted by members of the research team to notify them of the 5-year follow-up assessment. All participants in the original trial consented for their data to be stored and used to contact them again for research related to the Healthy Start, Happy Start study. Participants will be contacted by post and email to notify them of the opportunity to participate in the 5-year follow-up. All participants will be assessed in a one-year period of data collection, when children will be 6-9 years old. Participants will be scheduled to be seen at 5-years post-randomisation (±18 months).

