The primary aim is to estimate the probability that VIPP-SD is superior to usual care at 5 years post randomisation. A Bayesian mixed effects linear regression model will be used to calculate the probability that the PACS primary outcome score in the VIPP-SD group is greater than in the usual care group. The primary outcome at 5M, 24M and 5 years will be standardised in order to make Pre-PACS and PACs comparable in the model. The model will include treatment group, time, group by time interaction, baseline Pre-PACs score, the randomisation stratification variable center, and subject random effect (intercept and slope). Alongside the probability of superiority for VIPP, we will report the standardised between-arm mean difference with 95% credible interval. No multiple imputation will be used as 98% of the randomised sample will be included in the analysis model and the analysis is valid under a missing at random (MAR) assumption. This assumes the probability of missing data occurring is not dependent on the values of unobserved data, instead it is conditional on the observed variables included in the analysis models. We will perform a sensitivity analysis to the primary analysis to examine the MAR assumption using controlled multiple imputation. With controlled imputation we can induce missing not at random (MNAR) using a  $\delta$  approach (40). The parameter levels used for  $\delta$  will be pre-specified in the statistical analysis plan after discussion with the clinical team, likely values examined will correspond to +/- 25% and 50% of the treatment effect applied to those missing in both arms then each arm in turn to examine the possibility of the missing being informative in one arm only.

A supplementary analysis to the primary analysis will be performed in order to estimate the intervention effect in those that 'complied' (received four or more sessions of VIPP-SD) using a complier average causal effect (CACE) analysis. We will use either the calculation in a Bayesian framework guided by Imbens & Rubin (41) or the use of a two-stage least squares instrumental variable regression approach (42).

Healthy Start, Happy Start: Long-term follow-up - Study Protocol v 1.2

IRAS: 310487

V 1.2[tbc]

Protocol No: 1.2

Sponsor: University of Cambridge

V 1.2[tbc]

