A second analysis on the primary endpoint of this follow-up study (PACS at 5 years) using a Bayesian linear regression model with an informative prior distribution on the treatment effect model parameter will also be conducted. The informative prior distribution will be constructed based on the Pre-PACs results in the original trial using data and clinical judgment to translate to an approximate PACs distribution. Missing data will be imputed to allow all original participants to be included in the model. The results from this model will provide information of the difference between arms on the original PACs scale.

Analysis of continuous secondary outcomes will follow the principle of the primary analysis and use a Bayesian analysis with uninformative prior on the treatment effect. Where secondary outcomes are only collected at one time point (5-year follow up) multiple imputation will be used to include all randomised participants. The multiple imputation model will include the variables in the primary model and outcome and other variables as advised by the clinical study team. Where outcomes are repeatedly collected and the same we will use a Bayesian mixed effects longitudinal model. Probabilities for superiority of ViPP as well as treatment effect estimates and 95% credible intervals will be reported for all timepoints (5M, 12M and 5yrs). The results will be displayed visually to display the intervention effect and uncertainty around that estimate over time.

Binary and count outcomes will follow a similar principle for model covariate adjustment and imputation and with use of logistic and negative binomial regression models. CACE analysis will also be repeated for all secondary outcomes to obtain an estimate of the intervention effect in those that received it.

Issues with the availability and completeness of data obtained through data linkage are anticipated. Impacts of the COVID-19 pandemic mean that delays in accessing this data and a greater degree of missing data are likely. With these issues in mind, the main analysis of data will focus on data collected directly from participants. Secondary data analysis will be conducted on the routinely collected data accessed through the National Pupil Database and NHS Digital as an exploratory outcome if and when it becomes available. The exploratory analysis will follow the same principle of the secondary outcomes to compare between arm differences using adjusted regression modelling.

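### The primary model adjusts for baseline score and centre but not for child age, a small and avoidable loss of precision for child outcomes at 5 years

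*Protocol*

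**What the plan says.** Protocol section 9.2 specifies the primary model term by term. Besides the treatment arm, the time point and their interaction, the listed terms are "baseline Pre-PACs score, the randomisation stratification variable center, and subject random effect (intercept and slope". Time refers to the nominal points 5 months, 24 months and 5 years. Centre is the only stratification variable named, and age appears in no analysis model.

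For the other outcomes, section 9.2 says: "Analysis of continuous secondary outcomes will follow the principle of the primary analysis". Binary and count outcomes are to follow a similar principle of covariate adjustment. The clinical team may advise on further variables, but that opening concerns the multiple imputation model and not the analysis model.

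On age at entry, section 6.1 states: "A total of 300 families (child aged 12-36 months, and one or two participating caregivers) were recruited". On age at follow-up, section 6.1.1 states: "All participants will be assessed in a one-year period of data collection, when children will be 6-9 years old". On the visit window, the same section has this: "Participants will be scheduled to be seen at 5-years post-randomisation (±18 months". The background in section 1 says: "Behaviour disorders are more marked at age 7 (19". Among the exploratory outcomes, section 2.3.3 lists: "Language development assessed using a pictorial measure of vocabulary".

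**The concern.** The entry range alone puts the children up to 24 months apart in age. The one-year collection period and the ±18-month window add to that. The protocol itself treats age as relevant inside the assessed range: it describes behaviour disorders as more marked at 7, and section 7.2.1 changes the CHU9D respondent at that age. Baseline Pre-PACS does not replace an age term, because it was measured across the same 12-to-36-month range.

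If outcomes vary with age and the model has no age term, that variation adds to the residual. Credible intervals are then wider than they need be and, when there is a true effect, the expected probability of superiority is pulled towards 50%. That probability is the study's headline result. Age at entry was needed to recruit within the stated range, so the variable should already be held.

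**Working it through.** **Inputs from the protocol.** Section 9.1 gives n = 256 at 5 years and expected posterior probabilities of about 93%, 78% and 48% for effect sizes 0.22, 0.11 and 0. Section 6.1 gives 90% or more with 200 participants. Section 3 gives 1:1 allocation.

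**Assumptions.** Flat prior, normal approximation, outcome SD of 1. R² is the share of variance explained by the existing covariates and repeated measures; the protocol does not state it.

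**Formulas.** SE = 2·√((1 − R²)/n). Expected posterior probability = Φ(d / (SE·√2)).

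**Step 1: reproduce the plan's figures.** With R² = 0, SE = 2/√256 = 0.125 and the effect of 0.22 gives 89.3%. Reaching 93% needs SE = 0.1054, that is R² of about 0.29. That value was calibrated to the 93% and then tried on the other figures:

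| Setting | Protocol | Computed, R² about 0.29 |
|---|---|---|
| n = 256, ES 0.22 | 93% | 93.0% (calibrated) |
| n = 256, ES 0.11 | 78% | 77.0% |
| n = 256, ES 0 | 48% | 50.0% |
| n = 200, ES 0.22 | 90% or more | 90.4% |

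The fit is close enough to use as a base.

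**Step 2: add an age term.** If age explains a share p of the remaining variance, SE is multiplied by √(1 − p), and the equivalent sample size without the term is 256/(1 − p).

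| p | SE | Expected probability, ES 0.22 | Equivalent n |
|---|---|---|---|
| 0 | 0.1054 | 93.0% | 256 |
| 0.01 (r = 0.1) | 0.1049 | 93.1% | 259 (+1.0%) |
| 0.04 (r = 0.2) | 0.1033 | 93.4% | 267 (+4.2%) |
| 0.10 | 0.1000 | 94.0% | 284 (+11%) |

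Here r is the assumed correlation with age after the existing covariates, and p = r². A simulation of 4,000 trials per setting agrees: mean probability 93.9% and SE 0.1000 at p = 0.10. With no age effect the term costs almost nothing (SE 0.1053 without it, 0.1055 with it).

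**Step 3: how much of assessment age does age at randomisation carry?** Assume uniform distributions. Entry age has variance 24²/12 = 48 months² (SD 6.93 months, or 0.58 years). Its share of the variance in age at assessment is:

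- 48/(48 + 12) = 80% if families are seen in order of randomisation, leaving a 12-month spread in elapsed time (12²/12 = 12);
- 48/(48 + 48 + 12) = 44% if they are seen in random order (two-year recruitment plus one-year collection);
- 48/(48 + 108) = 31% if elapsed time fills the whole ±18 months (36²/12 = 108).

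If p = 0.04 refers to age at assessment, age at randomisation recovers 0.04 times these shares: 0.032, 0.018 or 0.012. The expected probability is then 93.3%, 93.2% or 93.1%. At p = 0.10 and a 44% share, the simulated SE is 0.1031, about 2% lower instead of 5%.

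**The case against.** The strongest reply is that nothing here is wrong. The model already adjusts for the baseline outcome and the stratification variable, and leaving out one more prognostic covariate is legitimate. For PACS, the one outcome whose model is fully written down, the gain is under half a percentage point at the assumed correlations. Section 9.2 also leaves further model detail to the statistical analysis plan. This limits the point to a minor improvement. It does not remove it, because the primary covariate list is stated in the protocol, and a plan that follows it will have no age term.

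A reader might infer more in four ways, none of which the protocol supports:

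- **Bias.** Randomisation balances age in expectation, and section 9.2 rightly says that chance imbalance does not invalidate the inference. The loss is one of precision.
- **A large gain for vocabulary and executive function.** Correlations of 0.3 to 0.5 would be worth 10% to 33% more children, since 1/(1 − r²) − 1 gives 9.9% and 33.3%. These correlations are assumptions. The protocol fixes neither a covariate list for these tasks nor whether their scores are raw or age-standardised.
- **Foundation Stage results.** Section 7.3.1 ties that assessment to the end of the first school year, so the age spread at the follow-up visit does not apply.
- **Every outcome.** There is no age argument for parental mood, anxiety, couple functioning or self-efficacy.

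**Conclusion.** The point holds as a small, nearly free improvement. Section 9.2 fixes a primary covariate list without child age and extends its principle to the secondary outcomes, while the children are 6 to 9 years old at assessment. For PACS the likely gain is about 1% to 4% in equivalent sample size, and somewhat less through age at randomisation alone. Strongly age-dependent child measures could gain more if raw scores are analysed, but the protocol does not allow that to be sized.

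These figures rest on assumed age-outcome correlations, an R² calibrated to the protocol's 93%, and uniform age and timing distributions. The 93% itself is not in dispute. The precision argument is for linear models. In logistic models, adding a covariate also changes the conditional effect being estimated.

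**What to change.** In section 9.2, add the child's age at randomisation as a prespecified covariate in the primary PACS model and in the 5-year models for child behaviour and directly assessed child outcomes. State that age-standardised scores will be used for child tasks where the instrument supplies them. Leave the models for parent outcomes as they are.

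Age at randomisation is preferable to age at assessment as the default because neither treatment nor visit scheduling can affect it, although it recovers less of the age variance. Whether its effect may differ by time point can be settled in the statistical analysis plan.

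The cost is a line or two of text and one parameter per linear model, with no new data. It should be settled before the first data extraction, so that the adjustment cannot look data-driven.

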## 9.3 Economic analysis

The long-term economic analysis will be a cost-utility analysis comparing VIPP-SD to usual care at 5-year follow-up with effects measured in terms of QALYs calculated from the CHU9D. The economic perspective will be the NHS/personal social services perspective, including those health and social care services provided within education settings. A secondary analysis will additionally include the cost of education facilities attended, given the age of the population.

Resource use, collected using the two versions of the CA-SUS, described above, will be costed using nationally applicable unit costs (e.g., NHS Reference Costs for hospital contacts, PSSRU Unit Costs of Health and Social Care for community health and social services, British National Formulary for medications). The intervention cost has already been calculated in the original trial and thus will not need costing. Discounting will be applied to both costs and outcomes, following the approach and the discount rate preferred by NICE at the time of the analysis (Note: NICE are currently reviewing the discount rate alongside other methods of economic evaluation and thus analyses will be finalised once this review is complete). The primary analysis will use costs generated from the detailed version of the CA-SUS focusing on all health and social care service use over a 3-month recall period. A sensitivity analysis will use costs generated from the shorter version of the CA-SUS focused on key services (high cost/high usage) over the full follow-up period from final 24-month follow-up to 5-year follow-up. Both analyses will include the costs of service use between baseline and 24-month follow-up estimated in the original trial.

Costs and outcomes will be compared in terms of mean differences and 95% confidence intervals from non-parametric bootstrap regressions (1,000 replications) to account for the non-normal distribution common to economic data. Cost-effectiveness will be assessed using the net benefit approach following standard approaches (43). A joint distribution of incremental mean costs and effects for the two groups will be generated using non-parametric bootstrapping to explore the probability that each of the treatments is the optimal choice, subject to a range of possible maximum values (ceiling ratio) that a decision-maker might be willing to pay for improvements in outcome (QALYs). Cost-effectiveness will be explored using incremental cost effectiveness ratios (44), with uncertainty represented by cost-effectiveness planes and cost-effectiveness acceptability curves (45). The approach to missing data and adjustment for baseline covariates will be in line with the clinical analyses described above.

Sensitivity analyses will test the sensitivity of the results to: a) the two approaches to parental-report resource use data collection using the CA-SUS (base case analysis: detailed over 3 months; sensitivity analysis: key service use over full follow-up period); b) the source of data on hospital contacts (base case analysis: CA-SUS; sensitivity analysis: HES data from NHS Digital, if available); c) the measure of effect (base case analysis: CHU9D; sensitivity analysis: primary clinical outcome measure); and d) the baseline utility values (base case analysis: SDQ mapping function; sensitivity analysis: values from the literature, if available).

Healthy Start, Happy Start: Long-term follow-up - Study Protocol v 1.2

## 10 DATA MANAGEMENT

#### 10.1 Data collection tools

#### 10.1.1 Source data

Paper records and secure electronic records of participant contact details will be kept. Pseudonymised data (linked by unique study code/identifier) will be entered directly onto the eCRF report form, either by the researcher conducting the assessment or the participating caregiver under the supervision of the researcher (dependent on which data/outcome measure is being collected as some of the proposed measures are researcher-led while others are participant self-report). For the majority of participants, the eCRF will be considered the source data as data will be entered directly onto the electronic database. Paper data collection will be offered as an alternative if requested. In these cases, the paper records will be considered the source data and will be transcribed onto the eCRF by the research assistants.

Multiple methods will be used to maximise the completeness of data (e.g., following up with teachers who have not returned their questionnaire via email).

## 10.1.2 Case report forms

Data will be entered onto an electronic Case Report Form (eCRF) developed in REDCap. Its use will be GDPR and GCP compliant. The eCRF will allow for audit trails to be kept to demonstrate the validity of the study (both during and after the study). Access will be restricted to trained staff with unique password-protected accounts. Forms completed directly by participants will be via a secure participant-specific link provided by email. The eCRF will only collect information directly relevant to the objectives and outcome measures detailed in the protocol. Identifiable data will not be recorded in the eCRF and participants will be identified by a unique trial ID only. Instructions for completion of the eCRF by researchers will be provided in a separate eCRF manual.

